13.1.2 Analyses

All analyses will be performed by NAPRTCS.

Amgen will receive reports on an annual basis, reflecting the (cumulative) two prior 6-month data collection periods. One final cumulative report will be received at the end of the 3-year study period.

13.2 Planned Methods of Analysis

Descriptive analyses will consist of summary statistics: mean, standard deviation, standard error, minimum, maximum, median, and quartiles for continuous variables, and frequency and percent for categorical variables.

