12. SAMPLE SIZE CONSIDERATIONS

The expected number of patients to be enrolled (during the years 2012 to 2015) is estimated to be between 1000 to 1500, with approximately 200 to 300 of these patients likely to receive cinacalcet over the life of the study. The objective of the study is to describe demographic characteristics, laboratory values, and events of interest (hypocalcemia, seizures, or infections requiring hospitalization) for patients in this population who do or do not receive treatment with cinacalcet.

The background rate of hypocalcemia and seizures is <1%. The rate of infection is expected to be higher, as infections are more common in the pediatric population.

Table 1 below illustrates the half-width of 95% confidence intervals for events with varying incidence rates, stratified by the expected number of cinacalcet (N = 300) and non-cinacalcet (N = 1200) patients:

Table 1. Confidence Intervals for Event Probabilities

N	True Probability of Event	95% CI Half-width
1200	0.1	0.017
1200	0.05	0.012
1200	0.01	0.006
1200	0.005	0.004
300	0.1	0.034
300	0.05	0.025
300	0.01	0.011
300	0.005	0.008

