13.1.1 Descriptive Analyses

Since the study is descriptive in nature, the analyses will describe the study population and outcomes in all study cohorts, for age < 21 years, for age < 18 years, as well as in different follow-up time periods (before and after cinacalcet exposure). This will include the following:

Approved

- total number of patients and total number of patient-years observation based on the annual data reporting periods, and for the cumulative 3-year study period
- estimation of rates of cinacalcet use based on the annual data reporting periods, and for the cumulative 3-year study period
- estimation of rates of AESI based on the annual data reporting periods, and for the cumulative 3-year study period
- proportion of patients who received at least 1 dose of cinacalcet within 7 days preceding an episode of hypocalcemia (from amongst all patients who developed hypocalcemia)

In addition, the following descriptive analyses using summary statistics will also be conducted:

- a tabular summary (eg, frequency, percent, rate) of categorical baseline demographic and clinical characteristics by cinacalcet-exposed and cinacalcet-unexposed
- for continuous variables (eg, age, weight, laboratory values) summary statistics for measures of central tendency (mean, median, SD, Q1, Q3, min, max) will be provided by cinacalcet-exposed and cinacalcet-unexposed

The cinacalcet utilization pattern will also be assessed (eg, dosing, duration of treatment).

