13.4 Annual Analysis

Annual reports from NAPRTCS are planned for this study. For each prespecified analysis, NAPRTCS will generate a report based on the available data in the annual

Approved

data reporting period, and cumulative for the entire 3 year study period. The analysis will be limited to the analyses described in [Section 13](#).

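### Section 12 describes precision by 95% confidence intervals, but Section 13, which limits the analysis, names no interval for adverse event of special interest (AESI) rates or proportions

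*Protocol*

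**What the plan says.** Section 12 expects that enrolment "is estimated to be between 1000 to 1500, with approximately 200 to 300 of these patients likely to receive cinacalcet". Its only statement of statistical precision is Table 1, which "illustrates the half-width of 95% confidence intervals for events with varying incidence rates". The table does this for 300 treated and 1200 untreated patients. The same section puts the background rate of hypocalcemia and seizures below 1%, and Section 14 expects few or very few events for the rare AESI.

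Section 13.1.1 plans "estimation of rates of AESI based on the annual data reporting periods, and for the cumulative 3-year study period". Section 13.2 lists the summary statistics. Continuous variables get, among others, a standard deviation and a standard error. The rest of the list reads "median, and quartiles for continuous variables, and frequency and percent for categorical variables". The synopsis treats the AESI as yes/no variables, so they fall in the categorical part.

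The synopsis refers the reader to Section 13 as the full description of the methods. Section 13.4 adds: "The analysis will be limited to the analyses described in" Section 13. Section 13.5 gives no further methods for the final report. Section 11 has the sponsor pass the annual reports to regulatory agencies.

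**The concern.** The protocol states its precision in one currency and plans its results in another. Table 1 leads a reader to expect event probabilities with 95% intervals, but the list of analyses contains no interval and no standard error for the AESI. Because that list is presented as full and then made the limit of the analysis, this is more than a detail left open for a later document.

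What is at stake is how rare events will read. The AESI were added at a regulator's request. A treated group without a seizure would be shown as 0%, and one with a single seizure as a fraction of a percent, with nothing beside the figure to show which risks the data exclude. Annual figures rest on less data than the cumulative ones and would be less precise still.

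**Working it through.** **Inputs.** From Section 12: N = 300 treated and 1200 untreated (Table 1); 200 as the lower expected number treated; event probabilities 0.1, 0.05, 0.01 and 0.005; background hypocalcemia and seizures below 1%. Exposed patient-years are not given, so 150, 300 and 600 are assumed below to show a range.

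**Step 1: reproduce Table 1.** The formula is the Wald half-width, 1.96 × √(p(1−p)/N).

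| p | N = 1200, computed | Table 1 | N = 300, computed | Table 1 |
|---|---|---|---|---|
| 0.1 | 0.01697 | 0.017 | 0.03395 | 0.034 |
| 0.05 | 0.01233 | 0.012 | 0.02466 | 0.025 |
| 0.01 | 0.00563 | 0.006 | 0.01126 | 0.011 |
| 0.005 | 0.00399 | 0.004 | 0.00798 | 0.008 |

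All eight rows agree, so Table 1 contains no arithmetic error.

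**Step 2: does the Table 1 formula suit rare events?** At N = 300:
- p = 0.01: 0.01 ± 0.01126, that is −0.13% to 2.13%.
- p = 0.005: 0.005 ± 0.00798, that is −0.30% to 1.30%.

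Both lower limits are negative. With no observed event the formula gives √(0 × 1/300) = 0, an interval of zero width. Carrying this formula into the reports would fail for the very events of interest.

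**Step 3: how likely are zero or very few events?** Expected treated events at N = 300 are 300 × 0.01 = 3 and 300 × 0.005 = 1.5. The chance of no event is (1−p)^N:
- N = 300: 0.99^300 = 4.9%; 0.995^300 = 22.2%.
- N = 200: 0.99^200 = 13.4%; 0.995^200 = 36.7%.

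**Step 4: what an exact interval would add.** These are Clopper-Pearson 95% limits; for zero events the upper limit is 1 − 0.025^(1/N).

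| Events / N | Bare figure | Exact 95% limits |
|---|---|---|
| 0/300 | 0% | 0 to 1.22% |
| 1/300 | 0.33% | 0.01 to 1.84% |
| 3/300 | 1.0% | 0.21 to 2.89% |
| 0/200 | 0% | 0 to 1.83% |
| 1/200 | 0.5% | 0.01 to 2.75% |
| 6/1200 | 0.5% | 0.18 to 1.09% |

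**Step 5: rates per patient-year.** With no event, the exact Poisson 95% upper limit is 3.69 divided by the patient-years. Under the assumed 150, 300 and 600 exposed patient-years this is 2.46, 1.23 and 0.61 per 100 patient-years.

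**The case against.** The strongest reply is that interval type and table layout commonly belong in a statistical analysis plan, which may exist and is not shown. No sentence in the protocol forbids an interval. Estimating a rate can naturally include one, and Section 12 suggests that intervals were in mind. The limiting sentence sits under the annual analysis and may restrict which analyses are run rather than how a result is displayed. Section 17.2 has the sponsor approve methods and report format before any report is generated.

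Part of this stands. One cannot conclude that the reports will certainly lack intervals, only that the protocol as written does not provide for them. It does not remove the point. The protocol calls Section 13 the full description, closes the list, and names a standard error for continuous variables but not for the AESI. The approval step is a convenient route to the fix; it does not put intervals into the plan.

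Three stronger readings are tempting and are not supported:
- *That the study was sized on interval width.* The number of patients is the expected registry enrolment. Table 1 illustrates the precision that follows, and no target width is set.
- *That Section 13 offers nothing but counts, percents and rates.* It also lists means, standard deviations, standard errors and quartiles, though for continuous variables.
- *That intervals are out of reach because Section 6 keeps the data with the registry.* Exact binomial limits need only events and patients, and exact Poisson limits only events and patient-years. Section 13 has these quantities reported, and Section 17.1 also mentions case-level data. The argument keeps some force only for recurrent hospitalized infections, where a valid interval needs the within-patient event pattern. The registry, which runs all the analyses, has that.

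It is also fair that a regulator could derive simple limits from a zero and its denominator, and that Section 14 already warns of low counts.

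**Conclusion.** The point holds as a mismatch within the protocol. Precision is described by 95% intervals in Section 12, and the list of analyses to which Section 13.4 confines the work names no interval or other uncertainty measure for AESI rates or proportions. It is worth correcting, but it does not undermine the design, and Table 1 is computed correctly.

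Its practical size is the gap between a bare 0% and an upper limit of 1.22% (300 treated) or 1.83% (200 treated). At a true risk of 0.5%, a zero count would occur in 22% of such studies with 300 treated patients and in 37% with 200. These figures assume a simple proportion of patients with at least one event and the protocol's expected treated numbers. The figures for rates rest on assumed patient-years.

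**What to change.** In Sections 13.1.1 and 13.2, state that:
- each AESI proportion is reported with an exact (Clopper-Pearson) 95% interval;
- each AESI rate per patient-year is reported with an exact Poisson 95% interval, except that recurrent hospitalized infections get a robust or patient-level bootstrap interval computed by the registry;
- these are given separately for the exposed and unexposed groups, in the annual and cumulative reports, with no between-group interval or test.

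The Wald formula behind Table 1 should not be used for these results, for the reasons in Step 2.

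An interval around a single group's rate is estimation, so it is consistent with the statements in the synopsis and Section 3.1 that no hypotheses are tested and no comparisons made. The cost is about two sentences and extra columns in tables the registry already produces. No new data are needed; only the infection interval takes a little additional programming.

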13.3 Missing Data and Loss to Follow-up

Data may be missing as previously discussed in [Section 9.1](#), and lead to bias.

Because entry of data into the NAPRTCS registry is completely voluntary, patients are lost to follow-up if there is a relocation, if they are no longer treated by a physician in a NAPRTCS affiliated institution, etc.

13.4 Annual Analysis

Annual reports from NAPRTCS are planned for this study. For each prespecified analysis, NAPRTCS will generate a report based on the available data in the annual

Approved

data reporting period, and cumulative for the entire 3 year study period. The analysis will be limited to the analyses described in [Section 13](#).

13.5 Final Analysis

A final report will be completed within 6 months after the end of the study (Q2, 2015). The final report will be comprehensive for all objectives and for the specific outcomes of interest.

14. STRENGTHS AND LIMITATIONS

Potential strengths (advantages) of the study include the following:

- utilization of the largest registry in North America for pediatric patients on dialysis
- prospective design allows for contemporary assessment of practice patterns
- utilizes existing data that are routinely collected from clinical practice settings reducing cost/burden on investigators and patients
- findings from this study may be evaluated collectively with those from other clinical studies conducted in other countries to complement a comprehensive global pediatric program to evaluate safety and efficacy

Potential limitations (disadvantages) of the proposed study include:

- small sample size due to the low prevalence of dialysis dependent CKD pediatric patients (estimated 2000 point prevalent patients in the United States)
- estimated event counts will be low or very low for rare AESIs
- voluntary nature of data entry into the NAPRTCS registry, which may result in missing data and information bias

15. REGULATORY OBLIGATIONS

This study is based upon routinely collected data from the NAPRTCS registry. Analyses using this data source will be conducted by NAPRTCS, whose investigators have access to the data through their respective institutions, with analysis reports presented to Amgen. Study results will only be presented in an aggregate form, and individuals will not be identified.

Informed consent for participation in the registry is obtained and maintained by NAPRTCS.

16. COMMUNICATION OF STUDY RESULTS

The health risk findings of the study associated with Amgen products must be reported to regulatory agencies according to local and international requirements. This study will conduct an assessment annually. The assessment results will be submitted to regulatory agencies accordingly.

Approved

17. ADMINISTRATIVE OBLIGATIONS

17.1 NAPRTCS Responsibilities

NAPRTCS, which comprises its study investigators, its Clinical Coordinating Center, and its Data Coordinating Center, is responsible for the following:

- maintaining investigational review board (IRB) and independent ethics committee (IEC) approvals
- prospectively collecting, managing, and organizing data to meet study objectives
- providing relevant case-level and aggregate clinical data, including all predefined AESI
- completing all statistical analyses
- developing ongoing and final study reports, and sending these completed reports to Amgen
- complying with required auditing procedures
- working with Amgen to prepare relevant publications

17.2 Amgen's Responsibilities

Amgen will provide financial support for this study. Amgen will work with NAPRTCS to ensure the study objectives are met. Other responsibilities of Amgen include the following:

- review and approve final study analyses, statistical methodologies and report format prior to report generation
- facilitate communication with regulatory authorities on study design, protocol and results, as applicable
- fulfill Amgen's regulatory responsibilities, including submission of reports, as required
- facilitate requests from regulatory authorities, as applicable
- collaborate with study teams to prepare relevant publications, as needed

Approved

